4.2.2.3 Duration of response

Descriptive data will be provided for the DoR in responding patients (ie median duration of response and 95% CIs) by treatment arm, including the associated Kaplan-Meier curves (without any formal comparison of treatment arms or p-value attached).

4.2.2.4 Proportion of patients alive and progression free at 12 months (APF12)

The proportion of patients alive and progression free at 12 months (i.e. at study day 366) will be summarised (using the Kaplan-Meier curve) and presented by treatment arm. For each treatment arm, the APF12 based on Kaplan-Meier method will be presented, along with its 95% confidence interval. The computation of the confidence interval will be based on a log(-log(.)) transformation.

4.2.2.5 Proportion of patients alive and progression free at 18 months (APF18)

The proportion of patients alive and progression free at 18 months (i.e. at study day 549) will be summarised (using the Kaplan-Meier curve) and presented by treatment arm. For each treatment arm, the APF18 based on Kaplan-Meier method will be presented, along with its 95% confidence interval. The computation of the confidence interval will be based on a log(-log(.)) transformation.

4.2.2.6 Time from randomisation to second progression (PFS2)

Time from randomisation to second progression (PFS2) will be analysed using the same methods as outlined for the analysis of PFS and adjusting for the same set of covariates, but no subgroup analysis will be performed. Medians and Kaplan-Meier plots will be presented to support the analysis. The sensitivity analysis outlined in Section 4.2.1.2 will not be repeated for PFS2 with the exception of a Kaplan-Meier plot of the time to censoring where the censoring indicator of PFS2 is reversed.

The number and percentage of subjects experiencing a PFS2 event and the type of progression (objective progression by RECIST, symptomatic progression, new or worsening of soft tissue/visceral or bone metastases or other) will also be summarised by treatment arm.

Time to second subsequent therapy or death (TSST)

For supportive purposes, the time to the start of second subsequent therapy will be analysed using the same methodology and model as that used for the analysis of PFS2. The HR for the treatment effect together with its 95% CI will be presented. In addition, a Kaplan-Meier plot of the time to the start of second subsequent therapy will be presented by treatment arm and the time between progression and starting second subsequent therapy will be assessed based upon the site investigator data defined date of progression. This will be summarised per treatment arm but no formal comparisons will be made. No multiplicity adjustment will be applied as this is viewed as a supportive endpoint.

4.2.2.7 Time to death or distant metastasis

TTDM will be analysed using identical methods as outlined for the analysis of PFS and adjusting for the same set of covariates, but no subgroup analysis will be performed. Medians and Kaplan-Meier plots will be presented to support the analysis. The sensitivity analysis outlined in Section 4.2.1.2 will not be repeated for TTDM with the exception of a Kaplan Meier plot of the time to censoring where the censoring indicator of TTDM is reversed.

4.2.2.8 Change in tumour size

The absolute values and percentage change in TL tumour size from baseline will be summarized using descriptive statistics and presented at each timepoint by treatment arm. The best change in TL tumour size from baseline, (where best change in TL size is the maximum reduction from baseline or the minimum increase from baseline in the absence of a reduction) will also be summarised and presented for each treatment arm.

Tumour size will also be presented graphically using waterfall plots for each treatment arm, to present each subject's best percentage change in tumour size as a separate bar, with the bars ordered from the largest increase to the largest decrease. Reference lines at the +20% and –30% change in tumour size levels will be added to the plots, which correspond with the definitions of progression and 'partial' response respectively. On each of the waterfall plots the PD-L1 status (positive vs negative), the histology categorization (squamous vs other) and the disease status at study entry (IIIA vs IIIB) of each patient will be indicated as appropriate. Additional waterfall plots showing percentage change in tumour size at specific timepoints may be produced if it is felt that these are warranted to provide greater clarity.

The above outputs will be programmed on data based upon BICR RECIST assessments. They will be repeated for the irRC (irRECIST 1.1) data obtained from BICR where tumour size is defined as the sum of the diameters of TLs and the new measured lesions.

4.2.3 Secondary patient reported outcome endpoints

The PRO endpoints that have been identified as primary are EORTC QLQ-C30 time to HRQoL deterioration for global health status and LC13 time to symptom deterioration for each of dyspnoea, cough, haemoptysis, and chest pain. These are not part of the main multiple testing procedure and as supportive endpoints will need a Bonferroni adjustment to the significance level to aid interpretation. Therefore, these 5 endpoints will be tested at a 1% significance level and 99% CIs will be produced.

The other time to symptom deterioration endpoints will be tested at a 5% significance level and 95% CIs will be produced.

4.2.3.1 EORTC QLQ-C30

Time to symptom deterioration will be analysed for each of the 3 symptom scales (fatigue, pain, nausea/vomiting) and the 5 individual symptom items (dyspnoea, insomnia, appetite loss, constipation, diarrhoea).

Time to HRQoL/function deterioration will be analysed for the 5 function scales (physical, role, emotional, cognitive, and social) and global health status/HRQoL. For treatment comparison, a stratified log-rank test will be used, as described for the primary analysis of OS.

The HR and 95% CI for each scale/item will be presented graphically on a forest plot.

A summary of the symptom improvement rate for each of the 3 symptom scales and the 5 individual symptom items will be produced. Similarly, a summary of HR QoL/function improvement rate for each of the 5 function scales (physical, role, emotional, cognitive, and social) and global health status/HR QoL will be produced. Symptom improvement rate and HR QoL/function improvement rate will be analysed by comparing between treatment arms using a logistic regression model adjusting for the same factors as the co-primary endpoints. The results of the analysis will be presented in terms of an odds ratio (an odds ratio greater than 1 will favour treatment A) together with its associated profile likelihood 95% CI (e.g. using the option 'LRCI' in SAS procedure GENMOD) and p-value (based on twice the change in log-likelihood resulting from the addition of a treatment factor to the model). The odds ratio and 95% CI for each scale/item will be presented graphically on a forest plot. If there are very few responses in one treatment arm, a Fisher's exact test will be considered.

For each of the 3 symptom scales (fatigue, pain, nausea/vomiting), 5 individual symptom items (dyspnoea, insomnia, appetite loss, constipation, diarrhoea), 5 functional scales (physical, role, emotional, cognitive, and social), and global health status/HR QoL, time to deterioration will be presented using a Kaplan-Meier plot. Summaries of the number and percentage of patients experiencing a clinically meaningful deterioration or death, and the median time to deterioration will also be provided for each treatment arm.

Summaries of original and change from baseline values of each symptom scale/item, the global HRQoL score and each functional domain will be reported by visit for each treatment arm. Graphical presentations may also be produced as appropriate. Summaries of the number and percentage of patients in each response category at each visit for each ordinal item (in terms of the proportion of patients in the categories of improvement, no change, and deterioration as defined in Section 3.3.1) will also be produced for each treatment arm.

A summary of compliance rate and evaluability rate will be provided for each treatment arm, by assessment time point and also for overall.

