3.3.1.3 Symptom Improvement Rate

The symptom improvement rate will be defined as the number (%) of patients with 2 consecutive assessments at least 14 days apart that show a clinically meaningful improvement (a decrease from baseline score ≥ 10 for EORTC-QLQ-C30 symptom scales/items) in that symptom from baseline. The denominator will consist of a subset of the ITT population who have a baseline symptom score ≥ 10 .

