3.3.1.4 HR QoL/Function Improvement Rate

The HR QoL/function improvement rate will be defined as the number (%) of patients with 2 consecutive assessments at least 14 days apart that show a clinically meaningful improvement (an increase from baseline score ≥ 10 for EORTC-QLQ-C30 functional scales and global health status/HR QoL) in that scale from baseline. The denominator will consist of a subset of the ITT population who have a baseline HR QoL/function score ≤ 90 .

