3.3.2.2 Symptom Improvement Rate

The symptom improvement rate will be defined as the number (%) of patients with 2 consecutive assessments at least 14 days apart that show a clinically meaningful improvement (a decrease from baseline score ≥ 10 for LC-13 symptom scales/items) in that symptom from baseline. The denominator will consist of a subset of the ITT population who have a baseline symptom score ≥ 10 as a lessening of 10 points is not possible at a baseline score of < 10 .

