4.2.1 Co-primary efficacy endpoints

4.2.1.1 Overall survival

The primary analysis of the co-primary endpoint, OS, will occur when approximately 491 deaths have occurred (approximately 70% maturity). OS will be analysed using a stratified log-rank test adjusting for age at randomisation (<65 vs ≥65 years of age), sex (male vs female), and smoking history (smoker vs non-smoker) for generation of the p-value and using the Breslow approach for handling ties (Breslow, 1974).

The effect of treatment will be estimated by the hazard ratio (HR) together with its corresponding (1-alpha adjusted)% CI and p-value for the ITT population.

The covariates in the statistical modelling will be based on the values entered into IVRS at randomisation, even if it is subsequently discovered that these values were incorrect. In addition a sensitivity analysis will be produced which use the covariates recorded in the CRF.

The HR and CI can be estimated from the stratified log-rank as follows (Berry et al 1991, Collett 2003, Sellke and Siegmund 1983):

$$HR = \exp\left(\frac{U}{V}\right)$$

$$95\% \text{ CI for HR} = \left(\exp\left\{\frac{U}{V} - \frac{1.96}{\sqrt{V}}\right\}, \exp\left\{\frac{U}{V} + \frac{1.96}{\sqrt{V}}\right\} \right)$$

Where $U = \sum_k U_k = \sum_k \sum_i (d_{1ki} - e_{1ki})$ is the stratified log-rank test statistic obtained from the SAS LIFTEST procedure, $\sqrt{V} = \sqrt{\sum_k V_k}$, is its standard deviation, k denotes the stratum and d_{1ki} and e_{1ki} are the observed and expected events in Group 1, stratum k.

Kaplan-Meier plots of OS will be presented by treatment arm. Summaries of the number and percentage of patients who have died, those still in survival follow-up, those lost to follow-up and those who have withdrawn consent will be provided along with the median OS for each treatment. The assumption of proportionality will be assessed.

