4.2.3.2 EORTC-QLQ-LC13

Time to symptom deterioration for each of the 6 individual symptoms (dyspnoea, cough, haemoptysis, chest pain, arm/shoulder pain, other pain) will be compared between treatment arms using a stratified log-rank test as described for the primary analysis of OS.

The HR and 95% CI for each scale/item will be presented graphically on a forest plot.

For each of the 6 symptoms items in LC13, time to deterioration in symptoms will be presented using a Kaplan-Meier plot. Summaries of the number and percentage of patients experiencing a clinically meaningful deterioration or death, and the median time to deterioration will also be provided for each treatment arm.

A summary of the symptom improvement rate for each of the 6 individual symptom items will be produced. The symptom improvement rate will be compared between treatment arms using a logistic regression model as described for EORTC-QLQ-C30. The odds ratio and 95% CI for each symptom will be presented graphically on a forest plot. If there are very few responses in one treatment arm, a Fisher's exact test will be considered.

Summaries of original and change from baseline values of each symptom (dyspnoea, cough, haemoptysis, chest pain, arm/shoulder pain, other pain) and each treatment-related side effect (sore mouth, dysphagia, peripheral neuropathy and alopecia) will be reported by visit for each treatment arm. Graphical presentations may also be produced as appropriate. Summaries of the number and percentage of patients in each response category at each visit for each ordinal symptom item (in terms of the proportion of patients in the categories of improvement, no change, and deterioration as defined in Section 3.3.2 will also be produced for each treatment arm.

A summary of compliance rate and evaluability rate will be provided for each treatment arm, by assessment time point and also for overall.

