The MMRM model will include the fixed, categorical effects of treatment, visit, and treatment-by-visit interaction, age at randomisation (<65 vs ≥65 years of age), sex (male vs female), smoking history (smoker vs non-smoker as well as the continuous fixed covariate of baseline score and the baseline score-by-visit interaction). Restricted maximum likelihood (REML) estimation will be used. An overall adjusted mean estimate will be derived that will estimate the average treatment effect over visits giving each visit equal weight. For this overall treatment comparison, adjusted mean estimates per treatment group and corresponding 95% CIs will be presented along with an estimate of the treatment difference, 95% CI and p-value

An unstructured covariance matrix will be used to model the within-subject error and the Kenward-Roger approximation will be used to estimate the degrees of freedom. If the fit of the unstructured covariance structure fails to converge, the following covariance structures will be tried in order until convergence is reached: toeplitz with heterogeneity, autoregressive with heterogeneity, toeplitz, autoregressive and compound symmetry.

Multiple imputation techniques for missing values may be considered to explore the robustness of any treatment effect.

An effect size estimate to interpret the magnitude of the effect and potential therapeutic benefit will be further specified in the PAP.

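### The logistic models for PRO improvement rates omit the baseline score; adding it would be a minor, low-cost gain in precision

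*SAP*

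**What the plan says.** SAP 4.2.3.1 analyses the QLQ-C30 symptom and QoL/function improvement rates "using a logistic regression model adjusting for the same factors as the co-primary endpoints" and reports an odds ratio, a profile-likelihood interval and a p-value. Those factors are set out in SAP 4.2.1.1: age group, sex and smoking history. SAP 4.2.3.2 compares the LC13 improvement rates "using a logistic regression model as described for EORTC-QLQ-C30". Neither section names the baseline score. Protocol 12.2.10.1 and 12.2.10.2 also specify logistic regression and list no covariates.

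The endpoint is binary. A patient improves if there are "2 consecutive assessments at least 14 days apart that show a clinically meaningful improvement" (SAP 3.3.1.3), meaning at least 10 points better than baseline.

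The denominators are restricted by baseline score:
- SAP 3.3.1.3, QLQ-C30 symptoms: "The denominator will consist of a subset of the ITT population who have a baseline symptom score ≥ 10".
- SAP 3.3.1.4, QoL and function: patients "who have a baseline HR QoL/function score ≤ 90".
- SAP 3.3.2.2, LC13: the same symptom cut-off, with the reason given "as a lessening of 10 points is not possible at a baseline score of < 10".

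Two other PRO models in the SAP do use baseline. The MMRM in 4.2.3.3 has the three stratification factors "as well as the continuous fixed covariate of baseline score and the baseline score-by-visit interaction". The EQ-5D-5L model in 4.2.9.1 adjusts for the baseline utility or visual analogue score.

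**The concern.** An outcome defined by change from baseline usually depends on the baseline value. Within the eligible range a patient with a worse starting score has more room to improve, and regression to the mean works in the same direction. If that association is appreciable, a logistic model without baseline tests the treatment effect with less power than one that includes it.

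The value is already in hand for every patient analysed, because eligibility for the denominator is decided by it. The SAP also treats baseline as worth adjusting for when it models change in the same kind of score. What is at stake is the precision of supportive PRO comparisons, not any confirmatory conclusion.

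**Working it through.** The documents give no power, effect size, improvement rate or baseline-outcome association for these endpoints, so there is no figure of their own to reproduce.

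**1. Models side by side**

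| Analysis | Outcome | Baseline score adjusted for? |
|---|---|---|
| Improvement rates, SAP 4.2.3.1 and 4.2.3.2 | change from baseline of at least 10 points, twice | no |
| MMRM, SAP 4.2.3.3 | change from baseline | yes, with its interaction with visit |
| EQ-5D-5L, SAP 4.2.9.1 | change from baseline | yes |

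Improvement rates cover 8 symptom scales or items + 5 function scales + global health status + 6 LC13 symptoms = 20 measures. The MMRM covers 7 of them, which leaves 20 − 7 = 13 with no baseline-adjusted treatment comparison.

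**2. Can every patient in the denominator improve by 10 points?**

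Attainable scores are 100·i/(k·r), for i = 0 to k·r, with k items of range r. The range is 3 for the 4-point items and 6 for the two 7-point items (protocol 6.5.1). The number of items for some scales is assumed.

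| k, r | Lowest eligible symptom score | Highest eligible function/QoL score | Room to improve |
|---|---|---|---|
| 1, 3 | 33.3 | 66.7 | 33.3 |
| 2, 3 | 16.7 | 83.3 | 16.7 |
| 3, 3 | 11.1 | 88.9 | 11.1 |
| 4, 3 | 16.7 | 83.3 | 16.7 |
| 5, 3 | 13.3 | 86.7 | 13.3 |
| 2, 6 | 16.7 | 83.3 | 16.7 |

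Every eligible patient has at least 11.1 points of room. The protocol's symptom cut-off (above 10) and the SAP's (10 or more) select the same patients, because no attainable score equals 10.

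Baseline can still affect how likely improvement is. On a single item, a patient at 33 improves only by reaching 0, whereas a patient at 100 improves by dropping to 67, 33 or 0.

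**3. How much power does adjustment add?**

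From the documents: 702 randomised at 2:1 (SAP 1.3), three binary covariates, and two-sided 5% (the SAP section 4 default, since no other level is given for improvement rates).

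Assumed: 350 or 500 eligible patients; control improvement rate about 25% with treatment odds ratio 1.9, or about 40% with 1.8; one 4-level item with baseline shares of 60/28/12% at scores 33/67/100.

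Data model: logit P(improve) = b0 + ln(OR per SD)·z + ln(treatment OR)·T, where z is the standardised baseline score and b0 is set to give the control rate. Each simulated trial was tested by the likelihood-ratio test for treatment, with and without z, in 2,000 trials per scenario. The Monte Carlo standard error of one power figure is about √(0.7 × 0.3/2000) = 1 point.

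| OR per SD of baseline | Power without baseline | Power with baseline | Gain, points |
|---|---|---|---|
| 1.0 | 74–87% | 75–88% | 0 |
| 1.5 | 70–86% | 71–87% | 0.5 to 1.6 |
| 2.0 | 63–80% | 68–83% | about 4 to 6 |
| 3.0 | 50–67% | 61–78% | about 11 to 12 |

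**4. Type I error**

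With no treatment effect, 500 patients, a 30% rate and 3,000 trials, the model without baseline rejected in 5.0% of trials at an OR per SD of 2 and again at 3. Adding baseline gave 4.9% and 4.6%.

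**The case against.** The case for leaving the model alone has several parts.

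- **Supportive status.** Improvement rates are outside the testing procedure of SAP 4.1.2 and are not among the five PRO endpoints that SAP 4.2.3 names as primary. The PRO measures listed under the secondary objective in SAP 1.1.2 are times to deterioration and WHO performance status. This stands, and it caps the importance of the point.
- **Consistency.** Using the co-primary factors throughout is a coherent prespecified choice, not an error. This also stands. Against it, the SAP departs from that choice in its two other change-from-baseline models.
- **A different odds ratio.** The odds ratio is non-collapsible, so adding baseline changes what is estimated. That is true, but the planned odds ratio is already conditional on three covariates. One more has to be stated, and it is no obstacle.
- **Form and sparsity.** A linear term is a modelling choice when a single item has only three eligible baseline levels, and the Fisher's exact fallback for sparse responses cannot carry a covariate. Both are fair. The simulation above fits baseline in the form that generated the data, so it flatters the gain slightly.

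Three stronger readings are tempting, and the documents do not support them:

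- A reader might infer that baseline decides whether improvement is possible. The denominators remove the patients for whom it is not.
- A reader might infer a large loss of power. One can obtain gains of 8 to 15 points (59% to 67%, 56% to 71%) by assuming a symptom model in which baseline explains 17–32% of the variance in improvement, but nothing in the documents fixes that strength.
- A reader might infer that chance baseline imbalance invalidates the comparison. Under randomisation the standard error already allows for it, and the simulated type I error was 5.0%.

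**Conclusion.** The point holds as a minor one. The improvement-rate models omit a covariate that bears directly on the outcome, is available for everyone analysed, and is used in the SAP's other change-from-baseline PRO models. The planned test remains valid; only precision is affected.

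The size rests on how prognostic baseline is among eligible patients, which is unknown. The gain is about 0 to 2 power points at an odds ratio per SD of up to 1.5, 4 to 6 at 2, and 11 to 12 at 3. The number eligible, the improvement rates, the treatment effect and the baseline distribution are all assumed. Adjustment was neutral or helpful in every scenario run. No conclusion on PFS, OS, OS24 or ORR is touched.

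**What to change.** In SAP 4.2.3.1, add the baseline score of the scale or item as a continuous covariate alongside age group, sex and smoking history, and let 4.2.3.2 inherit it for LC13. State that the odds ratio is then conditional on baseline as well, and that the Fisher's exact fallback stays unadjusted.

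The cost is one term in the model statement and a sentence of text. No new data are needed.

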4.2.3.2 EORTC-QLQ-LC13

Time to symptom deterioration for each of the 6 individual symptoms (dyspnoea, cough, haemoptysis, chest pain, arm/shoulder pain, other pain) will be compared between treatment arms using a stratified log-rank test as described for the primary analysis of OS.

The HR and 95% CI for each scale/item will be presented graphically on a forest plot.

For each of the 6 symptoms items in LC13, time to deterioration in symptoms will be presented using a Kaplan-Meier plot. Summaries of the number and percentage of patients experiencing a clinically meaningful deterioration or death, and the median time to deterioration will also be provided for each treatment arm.

A summary of the symptom improvement rate for each of the 6 individual symptom items will be produced. The symptom improvement rate will be compared between treatment arms using a logistic regression model as described for EORTC-QLQ-C30. The odds ratio and 95% CI for each symptom will be presented graphically on a forest plot. If there are very few responses in one treatment arm, a Fisher's exact test will be considered.

Summaries of original and change from baseline values of each symptom (dyspnoea, cough, haemoptysis, chest pain, arm/shoulder pain, other pain) and each treatment-related side effect (sore mouth, dysphagia, peripheral neuropathy and alopecia) will be reported by visit for each treatment arm. Graphical presentations may also be produced as appropriate. Summaries of the number and percentage of patients in each response category at each visit for each ordinal symptom item (in terms of the proportion of patients in the categories of improvement, no change, and deterioration as defined in Section 3.3.2 will also be produced for each treatment arm.

A summary of compliance rate and evaluability rate will be provided for each treatment arm, by assessment time point and also for overall.

